#### 8.7 Attach a Schedule of Activities (SOA) [Excel File](#) [\[Download the Template here: Schedule of Activities\]](#)

*Check to indicate that the SOA Excel File is attached →*

9.	Preparation/Handling/ Storage/Accountability of Investigational Drug, Biologic, or Device
	N/A - This study does not include any investigational products (e.g. drugs, devices or biologics)
	N/A - An Investigator Brochure is attached
	N/A - A Drug/Device Manual is attached
9.1. Acquisition and accountability	
State how the study intervention and control product will be provided to the investigator. Describe plans about how and by whom the study intervention will be distributed, including participation of a drug repository or pharmacy, and plans for disposal of expired or return of unused product.	
9.2. Formulation, Appearance, Packaging, and Labeling	
Describe the formulation, appearance, packaging, and labeling of the study intervention and control product, as supplied. Information in this section can usually be obtained from the IB or the package insert, or device labeling. This section should include the name of the manufacturer of the study intervention and control product.	

### 9.3. Product Storage and Stability

Describe storage and stability requirements (e.g., protection from light, temperature, humidity) for the study intervention and control product. For studies in which multi-dose vials are utilized, provide additional information regarding stability and expiration time after initial use (e.g., the seal is broken).

### 9.4. Preparation

Describe the preparation of the study intervention and control product, including any preparation required by study staff and/or study participants. Include thawing, diluting, mixing, and reconstitution/preparation instructions in this section. For devices, include any relevant assembly or use instructions.

## 10. Study Intervention Additional Details

### 10.1. Measures to Minimize Bias: Randomization and Blinding

This section should contain a description of randomization and blinding procedures (if applicable to the study design). It should include a description or a table that describes how study participants will be assigned to study groups, without being so specific that blinding or randomization might be compromised. Plans for the maintenance of trial randomization codes and appropriate blinding for the study should be discussed. The timing and procedures for planned and unplanned breaking of randomization codes should be included. Include a statement regarding when unblinding may occur and who may unblind. Provide the criteria for breaking the study blind or participant code. Discuss the circumstances in which the blind would be broken for an individual or for all participants (e.g., for serious adverse events (SAEs)). Indicate to whom the intentional and unintentional breaking of the blind should be reported.

Those with no preference for CAT or R-CAT will be Randomized, 1:1 done by statistician who has no patient contact through a random allocation program. If blinds are broken accidentally, new raters can be assigned, but blinds are kept by having raters and pill counters unaware of treatment group or study design.

### 10.2. Study Intervention Compliance

Define how adherence to the protocol (e.g., administration of study intervention, use of device,) will be assessed, and verified (if applicable, e.g., plasma assays, electronic monitoring devices, daily diaries).

All CAT and R-CAT providers will be UT Personnel and will receive regular supervision, audio taping of sessions for fidelity (5% reviewed per therapist), and photos of supports in home to complete quality assurance forms. Feedback will be provided to R-CAT providers to ensure high fidelity.

### 10.3. Permitted Concomitant Therapy

This section should be consistent with the medication restrictions in the inclusion/exclusion criteria previously listed. Describe how allowed concomitant therapy might affect the outcome (e.g., drug-drug interaction, direct effects on the study endpoints).

All concomitant therapies are allowed during the study.

### 10.4. Rescue Medicine

List all medications, treatments, and/or procedures that may be provided during the study for "rescue therapy" and relevant instructions.

N/A, no rescue medicine

## 11. Study Intervention Discontinuation

### 11.1. Discontinuation of Study Intervention

Describe the criteria for discontinuing the study intervention (e.g., halting rules), including any monitoring test(s) and associated clinical decision point(s). Include reasons for temporary discontinuation of the study intervention (e.g., type and quantity of adverse events), clearly stating the length of time, if applicable, and describe the data to be collected at the time of study intervention discontinuation and approaches for restarting administration of or re-challenging with study intervention.

None-- all individuals remain in standard community treatment with providers whether or not in this study.

### 11.2. Continued Follow-up Discontinuation of Study Intervention

Describe efforts that will be made to continue follow-up of participants who discontinue the study intervention, but remain in the study for follow-up, especially for safety and efficacy study endpoints (if applicable). Reasonable efforts must be made to undertake protocol-specified safety follow-up procedures to capture adverse events (AE), serious adverse events (SAE), and unanticipated problems involving risks to subjects or others (UPIRSOs).

None-- all individuals remain in standard community treatment with providers whether or not in this study.

## 12. Statistical Considerations

### 12.1. Statistical Hypotheses

State the formal and testable null and alternative hypotheses for primary and key secondary endpoints, specifying the type of comparison (e.g., superiority, equivalence or non-inferiority, dose response) and time period for which each endpoint will be analyzed.

**Aim 1: Examine the reach and acceptance of R-CAT and CAT for MCO members meeting entry criteria.** Barriers and facilitators for initial acceptance and those identified during treatment as well as treatment satisfaction, rates of dropout and reasons for dropout will be examined.

**Aim 2: Examine pre-implementation parameters of CAT and R-CAT** including case load differences for full time staff, provider and MCO assessment of barriers and facilitators and treatment related costs.

**Aim 3: Examine preliminary efficacy of R-CAT.** We hypothesize that both CAT and R-CAT will improve adherence to medication over time and that changes within each group will be of similar magnitude. We expect increases over time in automaticity/habit strength, and decreases in the overall level of psychiatric symptomatology.

### 12.2. Sample Size Determination

Include number of participants to recruit, screen, and enroll to have adequate power to test the key hypotheses for the study. Provide all information needed to validate your calculations and judge the feasibility of enrolling and following the necessary number of participants.

This is a pilot study and not powered for testing efficacy. Given that, we examined power for proportions using PASS (Aims 1 and 2). We will approach a minimum of 200 individuals to examine the acceptance rates of an initial offer of CAT versus R-CAT. We will be able to detect a 20% difference in proportions in acceptance with a power greater than .80; two-tailed alpha =0.05. We don't expect dropout rates to vary greatly between the 2 treatments but with 100 individuals and 50 in each of 2 treatment groups we will be able to detect a difference in drop out of at least 10% versus 30% at a power of .80; alpha=0.05. A smaller difference in dropout across 6 months would not be likely to impact decisions about which treatment to adopt and is not important to detect. Aim 3 examines differences from baseline within 4 groups (those with a preference for CAT; those with a preference for R-RCAT; those with no preference randomized to CAT and those with no preference randomized to R-CAT). With 25 per group for the randomized samples within each treatment SAS Power indicates that the smallest detectable effect would be for pill count adherence going from 70% to 85%. We would have power of .80 to detect difference of about 25% in pill count adherence proportions that that correlate .48 with probabilities of adherence from 60-85% in with a one tailed test at alpha of .05. <http://statulator.com/SampleSize/ss2PP.html>. This was verified using a simulation using 5000 replications. A one-tailed test is used as we are not interested in whether the intervention makes adherence worse.

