We will use components of the Reach, Effectiveness, Adoption, Implementation, Maintenance (RE-AIM) framework to compare Cognitive Adaptation Training (CAT) to Remotely delivered Cognitive Adaptation Training (R-CAT) 1-9 within a managed care organization (MCO), targeting members with serious mental illness (SMI) needing assistance with the regular taking of medication. In Part 1 of the research, **to assess both pre-implementation parameters and potential effectiveness, we will survey approximately 200-400 MCO members identified as having difficulty with medication follow through. CAT or R-CAT will be described in a randomized way and asked about acceptance, participants will then be told about the other intervention and asked about acceptance. Participants will then rate a series of statements covering dimensions of these treatments on the extent to which they agree/disagree with each statement. After the survey, participants will be offered the opportunity to participate in a research study examining CAT and R-CAT. Those who prefer one treatment over the other will get that**

treatment and those with no preference will be randomized 1:1 to CAT or R-CAT. This procedure will be followed and then altered as needed until 50 have accepted or been randomized to each group. Treatment will be offered for 6 months. In R-CAT interventions will be delivered primarily by remote and electronic means. Medication follow-through will be assessed using monthly unannounced pill counts. Automaticity (Habit formation), treatment satisfaction, barriers and facilitators to treatment and psychiatric symptoms will be assessed at baseline and every other month. Costs of providing CAT and R-CAT will be recorded including driving time, assisting with technology use, shipping, mileage, time in direct contact with member, time preparing for visits, and supports provided. Outcomes will be evaluated using within group repeated measures analyses. In sum, we are proposing to assess acceptability, feasibility, treatment satisfaction, pre-implementation parameters such as caseloads and costs, and preliminary efficacy of R-CAT compared to traditional home-delivered CAT.

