### 12.4. Statistical Analyses

Include analysis of primary efficacy endpoints, secondary endpoints, safety analyses, and any planned interim analyses

#### Aim 1

We will use X analyses to examine differences in proportions. We are interested in the rate of acceptance of CAT versus R-CAT when only one treatment is offered as an ecologically valid way of looking at acceptance rates in a real-world situation. In addition, we will examine acceptance of the 2nd treatment when the first is declined. We will also look at overall acceptance once both treatment options are explained (CAT, R-CAT, Neither) and whether the order in which the treatments were offered impacts acceptance. Finally, after both treatment options are presented, we will examine stated preference given an offer of both treatments (CAT, R-CAT, no preference, no

treatment desired). We will compare dropout by treatment group (CAT/R-CAT) using X2 analyses examining randomized and self-selected groups both combined and separated.

We will compare treatment satisfaction between groups using t-tests comparing CAT versus R-CAT examining randomized and self-selected groups both combined and separated.

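### The stated power of .80 for 10% versus 30% dropout with 50 per group is about .71 to .73 for the planned chi-square test; .80 is reached only one-sided.

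*Combined protocol and SAP*

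**What the plan says.** Section 12.2 gives two power statements for proportions, both attributed to PASS and to Aims 1 and 2. The first, on acceptance of the initial offer, is made "with a power greater than .80; two-tailed alpha =0.05". The second concerns dropout, for a total of 100 participants split equally between the two treatments. It claims: "we will be able to detect a difference in drop out of at least 10% versus 30% at a power of .80; alpha=0.05". The dropout statement does not say whether alpha is one-sided or two-sided. The section then explains the choice of target: "A smaller difference in dropout across 6 months would not be likely to impact decisions about which treatment to adopt".

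Section 12.4, Aim 1, names the test: "We will compare dropout by treatment group (CAT/R-CAT) using X2 analyses examining randomized and self-selected groups both combined and separated".

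Two further points bear on sidedness. Section 12.2 says that dropout is not expected to differ much between the treatments, so no direction is predicted. The only reason given for a one-tailed test comes at the end of Section 12.2. It says that a worsening of adherence is of no interest, which concerns Aim 3.

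**The concern.** A chi-square test on a two-by-two table rejects for a large difference in either direction, so at alpha 0.05 it is a two-sided test. With 50 per group and rates of 10% and 30%, power of .80 is more than that test delivers. The acceptance statement just before it is explicitly two-tailed, so a reader will take the dropout statement the same way.

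The figure matters because the proportion dropping out is a listed Aim 1 endpoint (Section 3), intended to inform future trials and adoption in the community. The plan also sets 20 points as the smallest difference relevant to a decision. If power at that threshold is overstated, a non-significant result can be taken as firmer evidence against an important difference than it is.

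**Working it through.** **Inputs.** Group size n = 50 (Section 12.2; Section 4 likewise recruits until there are 50 in each group). Dropout rates p1 = 0.10 and p2 = 0.30, alpha = 0.05, stated power .80 (all Section 12.2). Test: chi-square (Section 12.4).

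**Formula.** For two equal groups, with p̄ = (p1 + p2)/2 = 0.20:

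- Standard error under the null: SE0 = √(2 p̄(1 − p̄)/n) = √(2 × 0.20 × 0.80/50) = 0.0800
- Standard error under the alternative: SE1 = √((p1(1 − p1) + p2(1 − p2))/n) = √((0.09 + 0.21)/50) = 0.0775
- Power = Φ((|p2 − p1| − z × SE0)/SE1)

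**Step 1: reproduce the plan's figure.** With one-sided alpha 0.05, z = 1.645:

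(0.20 − 1.645 × 0.0800)/0.0775 = 0.883, so power = **.811**.

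The sample size for .80 is (1.645 × √0.32 + 0.842 × √0.30)²/0.20² = 48.4, or 49 per group. The stated .80 with 50 per group therefore matches a one-sided calculation. That this was its source is an inference; the document does not say so.

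**Step 2: the planned test.** With two-sided alpha 0.05, z = 1.960:

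(0.20 − 1.960 × 0.0800)/0.0775 = 0.558, so power = **.711**.

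The sample size for .80 is (1.960 × √0.32 + 0.842 × √0.30)²/0.20² = 61.6, or **62 per group**.

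**Step 3: does another two-sided method rescue the figure?** Power at 50 per group, 10% versus 30%:

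| Two-sided method | Power |
|---|---|
| Pooled normal approximation | .711 |
| Unpooled normal approximation | .733 |
| Arcsine approximation | .732 |
| Continuity-corrected approximation | .618 |
| Exact enumeration, uncorrected chi-square | .734 |
| Exact enumeration, likelihood-ratio test | .735 |
| Exact enumeration, unpooled z | .748 |
| Exact enumeration, continuity-corrected chi-square | .640 |
| Exact enumeration, Fisher's exact test | .640 |

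None reaches .80.

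**Step 4: what 50 per group can detect.** With 10% in one group, .80 power needs about 32.7% in the other by the pooled approximation. By exact enumeration of the uncorrected test, it needs about 32%. On that exact basis, about 60 per group would give .80 for 10% versus 30%.

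**Step 5: the separate comparisons.** Section 12.2 gives 25 per group for the randomised samples. The plan fixes no size for the self-selected groups; 25 each is an assumption that follows if the 50 in each treatment split evenly. With n = 25, SE0 = √(0.32/25) = 0.1131 and SE1 = √(0.30/25) = 0.1095:

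(0.20 − 1.960 × 0.1131)/0.1095 = −0.199, so power = **.42** (exact, uncorrected: .45).

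**Step 6: precision.** At 10% versus 30% with 50 per group, the half-width of the 95% confidence interval is 1.96 × √(0.09/50 + 0.21/50) = 0.152, or about 15 percentage points.

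**The case against.** The best defence is that the dropout statement gives alpha without a sidedness, whereas the sentence before it says two-tailed. The omission could be deliberate, and one-sided at 0.05 the figure is right. On that view the defect is an unstated sidedness, not wrong arithmetic. It is true that two-sidedness is inferred. But the one-sided reading does not fit the rest of the plan: the named test has no direction, none is predicted for dropout, and the one-tailed rationale covers adherence only. Even if one-sided was meant, the stated power belongs to a different test from the one in Section 12.4.

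A second objection is that .71 comes from an approximation, and exact enumeration of the uncorrected chi-square is kinder: power .73, about 60 per group needed, and a detectable contrast of 10% versus about 32%. That is fair, and a range is the honest statement. It does not bring the figure to .80.

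A third is that the consequence is small. The shortfall is 7 to 9 points of power, and Section 12.2 opens by saying that this is a pilot without power for efficacy. The size is indeed modest. That disclaimer covers efficacy, however, and the section then turns to the proportion comparisons as what the sample size can support.

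Finally, the plan claims no power for the separate comparisons and has no rule that non-significance means no difference. Both points stand. The 25-per-group figure contradicts nothing in the plan, and misreading of a null result is a risk rather than a stated intention.

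**Conclusion.** The statement is wrong as written. For 10% versus 30% dropout with 50 per group, the planned chi-square test at two-sided alpha 0.05 has power of about .71 (approximation) to .73 (exact, uncorrected), and .64 with continuity correction. The chance of missing a true 20-point difference is about 27% to 29% for the uncorrected test, against the 20% implied.

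This assumes that the chi-square test is used at two-sided 0.05, which is inferred from the test named and from the two-tailed statement beside it, and that 50 per group are reached and analysed. The conclusion does not depend on the choice of two-sided method. The figures for the separate comparisons (.42 to .45) also assume 25 per group, which the plan states only for the randomised samples.

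The error does not undermine the study or call for more participants, but the stated power should be corrected.

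**What to change.** In Section 12.2, state the sidedness and correct the figure, for example: with 50 per group and two-sided alpha 0.05, power is about 0.71 (0.73 by exact calculation) for 10% versus 30% dropout, and the difference detectable with power 0.80 is 10% versus about 33% (about 32% by exact calculation). If a one-sided test was intended, say so, give the direction and the reason, and change the test in Section 12.4 to match.

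In Section 12.4, add that the dropout difference will be reported with its 95% confidence interval (about ±15 points at these rates), so that a non-significant result is not taken to rule out an important difference. Note there that the separate comparisons have power of about 0.42 to 0.45 if there are 25 per group.

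The cost is one sentence in each section and a less favourable power figure. Keeping .80 power for 10% versus 30% would instead need 62 per group, or 124 in total (2 × 62), which is hard to justify for a pilot.

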#### **Aim 3**

The primary variable is in-home pill count percent established on each monthly visits or virtual visits. Secondary variables are MPR, PDC, SRHI automaticity SRHI total score, Symptoms and SOFAS scores. We will examine within group change and effect sizes using a likelihood-based population-averaged (marginal) generalized linear regression model with repeated measures as implemented in the SAS GLIMMIX procedure specifying binomial (proportions) or normal (scales) as appropriate. A-likelihood based regression model with repeated measures makes the best use if all the information including cases with incomplete or missing data. The primary hypothesis tests planned contrasts at the final assessment of within-arm change and the difference between arms.

We will examine trajectories for 4 groups; the 2 groups with a preference (for either R-CAT or CAT) that were self-selected the 2 groups who did not indicated a preference and were randomized to either CAT or R-CAT. We will examine differences in baseline characteristics between the two groups with preferences as these differences may be related to outcome in the self-selected samples.

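### Section 12.2 gives two irreconcilable detectable changes in pill-count adherence for 25 per group (15 points and about 25 points), and the 15-point figure does not reproduce

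*Combined protocol and SAP*

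**What the plan says.** Section 12.2 (Sample Size Determination) opens its answer with a caveat: "This is a pilot study and not powered for testing efficacy". For Aim 3, which looks at change from baseline within each of four groups, it then makes two statements about pill-count adherence.

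- **Statement A.** Citing the SAS power software and 25 people in each randomized group, the plan reports: "the smallest detectable effect would be for pill count adherence going from 70% to 85" (per cent). That is 15 points. The sentence names the sample size and the software, but no power, alpha, correlation or SD.
- **Statement B.** "We would have power of .80 to detect difference of about 25% in pill count adherence proportions that that correlate .48". The rates given are 60% and 85%, and the test is one-tailed at .05. That is 25 points. A web calculator is linked.

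No new sample size is introduced between the two. After statement B and the link comes "This was verified using a simulation using 5000 replications", without saying which figure was verified. A closing sentence explains why the test is one-tailed.

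Section 8.6 defines the endpoint as a percentage for each person: pills presumed taken over pills prescribed. Section 12.4 (Aim 3) plans a repeated-measures GLIMMIX model, "specifying binomial (proportions) or normal (scales) as appropriate". No SD for pill-count percent is given anywhere.

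**The concern.** If 15 points is the smallest change that 25 people can detect, a 25-point change ending at the same 85% must have power well above .80 under the same method. If 25 points is what gives power .80, 15 points cannot be detectable at that level. The different starting values (70% and 60%) do not explain the gap.

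These are the plan's only statements of the within-group change that its primary Aim 3 endpoint can detect. The pilot is meant to inform later trials, so the figure affects how a non-significant within-group result is read. A true 15-point rise was either likely to be found or about as likely to be missed as found, and the reader cannot tell which.

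**Working it through.** **Inputs.** From Section 12.2: n = 25 per randomized group, correlation .48, one-tailed alpha .05, power .80, and the rates 60%, 70% and 85%. Only statement B ties alpha, power and correlation to a figure, so they are the only inputs on which statement A can be tested.

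**Method: paired proportions.** With baseline rate p1, final rate p2 and correlation r:

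- both adherent: p11 = p1·p2 + r·√(p1·(1−p1)·p2·(1−p2))
- discordant cells: p1 − p11 (worse) and p2 − p11 (better); s is their sum and d = p2 − p1
- pairs needed: n = (1.645·√s + 0.8416·√(s − d²))² / d²
- power at n = 25: Φ[(d·√25 − 1.645·√s) / √(s − d²)]

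**Step 1: statement B (60% to 85%).**
- p11 = .510 + .48 × .1749 = .5940; cells .0060 and .2560; s = .2621, d = .25
- n = (1.645 × .5119 + 0.8416 × .4467)² / .0625 = **23.7 pairs** (27.6 with continuity correction)
- power at 25 = Φ[(1.25 − .842) / .447] = **.82**

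This agrees with the plan's 25 per group and power .80.

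**Step 2: statement A (70% to 85%), same inputs.**
- p11 = .595 + .48 × .1636 = .6735; cells .0265 and .1765; s = .2029, d = .15
- n = (1.645 × .4505 + 0.8416 × .4248)² / .0225 = **53.6 pairs** (60.1 with continuity correction)
- power at 25 = Φ[(.75 − .741) / .425] = **.51**

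**Step 3: does another correlation rescue it?** The correlation is largest when nobody worsens, so p11 = .70 and r = (.70 − .595)/.1636 = .64. Then n = 39.1 pairs and power is .62.

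**Step 4: does the choice of test matter?** Power at n = 25, one-tailed .05:

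| Change, correlation | Normal approx. | Exact McNemar | Mid-p | Uncorrected McNemar |
|---|---|---|---|---|
| 60% to 85%, .48 | .82 | .75 | .87 | .92 |
| 70% to 85%, .48 | .51 | .29 | .45 | .54 |
| 70% to 85%, .64 (maximum) | .62 | .32 | .53 | .75 |

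No version reaches .80 for 70% to 85%. A simulation of 200,000 samples of 25 agrees: for 70% to 85%, .293 exact and .540 uncorrected; for 60% to 85%, .751 and .919. With 5000 replications the Monte Carlo standard error at power .5 is √(.25/5000) = .007, so a simulation of the plan's size under these inputs would have shown the shortfall.

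**Step 5: what is detectable at .80?** For a change ending at 85% with n = 25 and correlation .48, the smallest rise is about 24 points by normal approximation (from 60.8%), 26 by the exact test and 21 by the uncorrected test. The plan's figure of about 25 points lies in that range; 15 does not.

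**Step 6: the percentage as a continuous measure (assumption: the SD is not in the documents).** A paired t-test with n = 25 and one-tailed .05 has power .80 at a standardized change of .512.
- The SD of change needed for 15 points is 15/.512 = 29.3. With correlation .48 this is a per-visit SD of 29.3/√(2 × .52) = 28.7.
- Power for 15 points is .98, .78 and .57 at an SD of change of 20, 30 and 40.
- At an SD of change of 29.3, power for 25 points is .99.

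This reading can support statement A, but statement B then no longer describes the .80 threshold.

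**The case against.** The strongest reply is that statement A never mentions power .80. It may mean the smallest observed change that would reach significance. With the cells for 70% to 85%, that threshold is 1.645 × √(.2029/25) = .148, or 14.8 points, which is very close to 15. Both statements could then be true under the same inputs, as a significance threshold and an .80-power effect. This is a plausible account of where the figure came from, but the plan does not say so. It would also mean that a true 15-point change has only about a 50% chance of detection, which is not what readers of a sample-size section take a smallest detectable effect to be.

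The inputs tested here also come from statement B, which cites a different tool, and a paired binary test may not be the planned analysis of a per-person percentage. Both points stand. They are why the 15-point figure is called unsupported rather than disproved, and why the continuous reading was worked through.

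A third possibility is that statement A used 50 per treatment, pooling preference and randomized participants. Power is then .77 by the standard formula and .80 with unpooled variance, but the sentence specifies 25 per group.

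Finally, this is a pilot with an explicit caveat, and no decision rule uses the 15-point figure. That limits the consequence but does not reconcile the two statements.

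**Conclusion.** The concern holds. The two statements cannot both be the change detectable with power .80 at 25 per group. Under the only inputs given, treated as paired proportions, 60% to 85% reproduces (23.7 pairs; power .82, or .75 to .92 depending on the test). A change from 70% to 85% does not: it needs 53.6 pairs, about twice the 25 available, and has power .51 (.29 exact, .54 uncorrected). No feasible correlation brings it to .80.

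The 15-point figure could be right on a continuous scale if the SD of change is about 29 points or less, but that SD is an assumption the documents neither give nor imply. The practical weight is modest: it affects the interpretation of Aim 3 results, not the conduct of the study. It should be fixed.

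**What to change.** In Section 12.2, keep one detectable effect for Aim 3. State its n, power, alpha, sidedness, test, and correlation or SD, on the scale on which the Section 12.4 model will analyse pill-count percent. Remove 70% to 85% as the smallest detectable effect unless the SAS Power test and the inputs that give it power .80 are stated. If it was meant as a significance threshold, label it as one. Say which figure the 5000-replication simulation checked, and with what test.

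If the paired-proportion inputs are kept, possible wording is: *With 25 per randomized group, a correlation of .48 and a one-tailed alpha of .05, power is about .80 to detect a rise in pill-count adherence from 60% to 85%.* The test should be named with it, since power runs from .75 to .92 across tests. If the percentage will be modelled as continuous, give the assumed SD of change and its source instead.

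The cost is rewording one section, with no extra participants and no change to procedures. The stated detectable effect may become less favourable, at about 25 points rather than 15.
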